2.3.5 Gene Expression Data

The PAXgene Blood RNA Tube (Catalog No. 762165) was at room temperature (18-25C) and properly labeled for patient identification. The CRC collected one 2.5 ml of blood into one tube using the standard technique for BD Vacutainer® Evacuated Blood Collection Tubes.

2.3.6 After Blood Collection

The CRC inverted the PAXgene Blood RNA Tube 8 to 10 times and stored the PAXgene Blood RNA Tube upright at room temperature (18°C–25°C) for a minimum of 2 hours and a maximum of 72 hours before processing or transferring to refrigerator (28°C) or freezer (-20°C). After 48 hours in freezer (-20°C) the blood samples were transferred and stored in a freezer (-80°C) until they were prepared for RNA sequencing.

Transport Collected Blood Samples: Blood samples were transported to SC2 Core lab for processing and library preparation for RNA sequencing.

2.4 Retention Strategies

The PI and CRC maintained contact with the study participants by telephone, in person, or email to encourage retention in the study. In addition, to providing log-book instructions and meeting time reminders during this contact, the CRC or PI encouraged questions and sharing on how they are experiencing the research study with goal of establishing a therapeutic alliance between the research staff and the study participants. The study participants were also encouraged to initiate contact with the PI or CRC with any questions or concerns by phone, email, or in person.

2.4.1 Sample Size Justification

The enrollment goal of 40 participants followed the guidelines of Browne [37] to formulate samples sizes for pilot studies. This was the target for recruitment with an expected attrition rate of 20%. Although 27 participants were consented, only 14 completed the study. The 14 who completed the study met the standards established by Julious [38] for pilot study sample sizes. Browne and Julious [37, 38] provided sample size calculation guidelines for pilot studies designed to collect preliminary data for a clinical trial.

2.4.2 Hypothesis Testing Data Analysis Plan

This study utilized the Paired Sample t-test of the SPSS statistical program to analyze the primary outcome changes in cognitive function anxiety, depression, and sleep quality over an 8-week period. Changes in BDNF, NF- κ B1, and TP53 gene expression results were analyzed using the paired sample t-test in SPSS to determine if the means of the pre- and post-MM gene expression data were significantly different.

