Cover Page

02/16/2022

GME Study

Gene Expression, Meditative Movement, and Emotional Distress (GME)

NCT04213872

Study Protocol and Statistical Analysis Plan

2. Method

This was a single-group pilot study testing the effects of 8 weeks of MM practice on changes in cognitive function, anxiety, sleep quality, depression, and selected gene expression factors. The enrollment goal was to consent and assign forty BCSs to an eight-week MM program. Measures on cognitive functioning, associated symptoms/conditions, and gene expression data were collected before and after the 8-week MM program. This study utilized the Paired Sample t-test of SPSS [22] to report p-values from the analysis of pre- and post-MM intervention changes in the cognitive functioning, associated symptoms/conditions, and gene expression data. This study was approved by both the IRB committees at Pomona Valley Hospital Medical Center (PVHMC as the primary IRB) and at Arizona State University (ASU as the secondary IRB).

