2.4.3 Missing Data

Participant responses were reviewed for missing data and participants were given an opportunity to complete overlooked questions or indicate a preference not to answer during the data collection session. All analyses were conducted on participants who completed the intervention. If post-intervention data was unavailable, missing data were not imputed. As a small pilot study to detect trends in change from pre- to post-intervention, we do not expect there to be a systematic bias introduced by the data loss of a small number of participants. One study participant did not complete her post-MM program WAIS-III measure and did not submit her MM logbook due to schedule conflicts.

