2.4.4 Secondary Outcomes

Peripheral blood samples were collected before and after the 8-week MM program. The gene expression data was processed and analyzed by the bioinformatics team at the Single-Cell, Sequencing, and CyTOF Core (SC2), Children's Hospital Los Angeles (CHLA), Los Angeles. These data were analyzed using the paired sample t-test in the IBM SPSS Statistics program.

RNA sequencing: Sequencing libraries were prepared from previously purified RNA using the Illumina TruSeq Stranded mRNA Library Prep kit following the manufacturer's instructions. Sequencing was performed on a NextSeq 500 platform using 2 \times 75bp chemistry [39].

Gene Expression data analysis: Quality control and adapter trimming was performed using trim galore (v0.4.2) with default parameters [40]. Reads were aligned to the GRCh38 reference genome and transcriptome using HISAT2, v2.1.0 [41], and transcript quantification was performed using featureCounts, v1.5.1 [42]. Differential expression analysis was performed using the 'DESeq2' R package, v1.16.1, [43] and a rank score calculated

as $-\log_{10}(\text{q-val}) * \text{sign}(\log_2 \text{FoldChange})$ was used as input to the GSEA Preranked tool for pathway analysis [44].

The DESeq2 data were used to identify the gene expression changes over the 8-week MM program. DESeq2 (differential expression sequence) files are TMM (weighted trimmed mean of the log expression ratios - trimmed mean of M values) normalized count per million reads.

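### Does the unstated scale of the paired t-test for BDNF, NF-κB1 and TP53 call for a change to the analysis?

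*Combined protocol and SAP*

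**What the plan says.** The combined protocol and SAP names one test for the three genes in three places, and none of them gives a scale.

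- Section 2 (Method), covering all outcomes including gene expression: "This study utilized the Paired Sample t-test of SPSS [22] to report p-values from the analysis of pre- and post-MM intervention changes".
- Section 2.4.2 (Hypothesis Testing Data Analysis Plan), for the three genes by name: "gene expression results were analyzed using the paired sample t-test in SPSS to determine if the means of the pre- and post-MM" values were significantly different.
- Section 2.4.4 (Secondary Outcomes), after the blood samples: "These data were analyzed using the paired sample t-test in the IBM SPSS Statistics program".

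Section 2.4.4 gives a single expression unit, for the DESeq2 output: these "files are TMM (weighted trimmed mean of the log expression ratios - trimmed mean of M values) normalized count per million reads". It does not say that these values went into SPSS, or whether they were logged first.

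On numbers, section 2.4.1 (Sample Size Justification) says "Although 27 participants were consented, only 14 completed the study", and section 2.4.3 (Missing Data) says "All analyses were conducted on participants who completed the intervention". So 14 is the upper limit for RNA pairs; the actual number is not given.

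**The concern.** Expression values often differ several-fold between people, and their noise often grows with level. On CPM, a few women with high expression can then dominate the standard deviation of the differences and hide a change that is consistent as a ratio. A log transform removes that dominance. Section 2.4.4 appears to think in ratios, since its description of the normalisation refers to log expression ratios and its pathway score refers to a log2 fold change. A test on raw means would then look out of step with the rest of the section.

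Two things would be at stake. With at most 14 pairs, whether a gene reaches p<0.05 could depend on a choice the reader cannot see. The sample size also rests on guidelines for "pilot studies designed to collect preliminary data for a clinical trial", and a later trial cannot plan from a mean change or SD whose scale and number of pairs are unknown.

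**Working it through.** **Plan's own figure.** The plan states no power, effect size or SD for gene expression, so there is nothing to reproduce. Its only sample-size figure is 40 with 20% attrition (40 × 0.8 = 32 completers), taken from a pilot guideline.

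**Inputs.** From the documents: at most 14 pairs, and a paired t-test. Assumed: two-sided 5% level, typical expression of 40 CPM, library size 15 to 35 million reads, Poisson counts. The log scale is log2(CPM + 0.5). Log-SDs are natural-log unless stated, and three figures separated by slashes are for between-person log-SD 0.3 / 0.6 / 1.0. There were 40,000 simulated datasets per scenario.

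**1. Is the stated test valid?** With no change and equal spread at both visits, the CPM test rejects in 4.5 / 4.2 / 2.9% of datasets and the log2 test in 4.8 / 5.1 / 5.1%. Neither is inflated.

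**2. Noise proportional to level.** Take a 1.3-fold change and within-person log-SD 0.3 at each visit.

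- Log scale by formula: standardised change = ln(1.3) / (0.3 × √2) = 0.262 / 0.424 = 0.62. With 14 pairs the noncentrality is 0.62 × √14 = 2.31 on 13 degrees of freedom, giving power of about 57%.
- Simulation: 52 / 43 / 29% on CPM against 57 / 57 / 56% on log2, a gain from logging of 5 / 14 / 27 points.
- Over a grid of 27 combinations of fold change, within-person and between-person SD, the gain runs from 0.2 to 33 points.

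The largest gain of these three needs a between-person log-SD of 1.0, which is a ratio of e² ≈ 7.4 between a woman one SD above the middle and one an SD below.

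**3. Noise constant in CPM.** Take a shift of 6 CPM with noise SD 5 CPM at each visit. Power is 81 / 81 / 81% on CPM against 78 / 68 / 53% on log2, so logging costs 3 / 13 / 28 points.

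**4. A separate set of assumptions.** Here the log test is set to about 80% power, with paired log2 SD 0.5, noise proportional to level and 14 pairs. CPM power is 79, 78, 74, 61 and 45% at between-person log2 SD 0.1, 0.3, 0.5, 1.0 and 1.5. With constant noise the order reverses: 90% on CPM against 68% on log2 at between-person log2 SD 1.0.

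**5. Is there a conflict inside section 2.4.4?** The pathway score is −log10(q) × sign(log2 fold change). Only the direction of change enters; the size of the ratio is discarded. The mention of log expression ratios expands the name of the normalisation, and the same sentence gives the resulting unit as CPM. Section 2.4.2 speaks of means, and a t-test on logged values also compares means. The section therefore documents no log-ratio analysis from which the t-test departs.

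**The case for a change.** The strongest case for acting is that disclosure is cheap and the choice can matter. In the proportional-noise scenario the two scales disagree on p<0.05 in 10 / 19 / 31% of datasets, and proportional noise is a reasonable expectation for sequencing counts. A later trial would need the SD of the log change and the number of pairs, and the documents supply neither. The remedy would be a sentence plus a labelled post hoc log2 result for each gene, with the existing test left as the result of record.

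Part of this stands. The scale and the number of pairs are not stated, and a report of the results is more useful with both. The analysts hold the SPSS file, so both facts can be recovered without touching the analysis. A geometric mean fold change with its 95% CI and the SD of the log2 changes would be handy planning data.

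The rest does not amount to a change in the analysis. If the values were already logged, there is nothing to redo. If they were CPM, the proposal itself leaves the stated result in place, so the conclusion for each gene stays the same. The extra test has a small price: counting significance on either scale rejects in about 6% of null datasets per gene. It also answers a different question, about geometric rather than arithmetic means. As for the number of pairs, section 2.4.3 mentions one completer with missing items (WAIS-III and logbook) and no missing RNA, so 14 is the natural reading, though it is not confirmed.

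**Conclusion.** No change to the plan follows. The paired t-test is an acceptable test for these genes on CPM or on a log scale, and choosing between them is a fair trade-off that depends on how noise behaves in the data. The documents give no expression values or SDs, so even the sign of the difference cannot be settled: from 33 points in favour of logging to 28 points against it. It is about 3 to 5 points in the two main scenarios when women have similar expression levels (between-person log-SD 0.3). All of these figures rest on assumed inputs apart from the limit of 14 pairs. The finding on type I error assumes equal spread at the two visits.

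The setting points the same way. Gene expression is a secondary outcome of a completed single-group pilot, and power lost in a finished study cannot be recovered by a log2 test chosen after the fact. What is left is a missing detail, the scale and the number of RNA pairs per gene, which the analysts can state when they report.

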2.1 Study Population

2.1.1 Eligibility Criteria

Inclusion criteria: minimum 45 years of age; female patients diagnosed with breast cancer, stages 0–III; between six months and five years past primary treatment; ability to speak or understand English; and post-menopausal for at least one year. Exclusion criteria: Women who were unable to stand (e.g., wheelchair or walker bound); patients who were too weak or ill; patients on antibiotics; women working on night shift; and patients with anemia or uncontrolled diabetes. Pregnant women, mentally disabled persons, and prisoners were excluded.

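### Gene expression is measured in unfractionated whole blood with no check on leukocyte mix, so a mean shift in cell proportions could appear as a change in gene expression; the existing RNA-seq data allow a check

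*Combined protocol and SAP*

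**What the plan says.** Section 2.3.5 describes the specimen: "The CRC collected one 2.5 ml of blood into one tube using the standard technique". Section 2.3.6 covers inversion, storage and freezing, and then states: "Blood samples were transported to SC2 Core lab for processing and library preparation for RNA sequencing". Neither section describes cell separation. The measures in section 2.3 are demographics, self-report and cognitive data, and blood for gene expression; no white-cell differential is among them.

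On analysis, section 2.4.2 states: "Changes in BDNF, NF- κ B1, and TP53 gene expression results were analyzed using the paired sample t-test in SPSS", the purpose being "to determine if the means of the pre- and post-MM gene expression data were significantly different". No covariate is mentioned. Section 2.4.4 adds: "Differential expression analysis was performed using the 'DESeq2' R package", followed by preranked GSEA, with no design formula or covariate. The data scale is TMM "normalized count per million reads". Reads are aligned to the whole genome and transcriptome.

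The nearest thing to an allowance is in section 2.1.1, which excludes patients who are too weak or ill, on antibiotics, working night shifts, anemic or with uncontrolled diabetes.

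**The concern.** The bulk value of a gene in whole blood is an average over cell types, weighted by how much of each is in the tube. A difference between pre and post means therefore mixes two things: a change in expression within cells, and a change in which cells were sampled.

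Nothing in the plan separates them:

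- Pairing removes stable differences in cell mix between women, but not a shift within a woman.
- TMM normalisation handles library size and RNA composition, not cell proportions.
- The exclusions apply at entry. They narrow some causes of a shift, but they do not measure the mix, and no recheck at the post draw is stated.
- There is no control arm, so a mean shift from any cause goes into the pre-post difference. The draws are 8 to 12 weeks apart (8 weeks plus up to two weeks at each end, section 2.3).

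At stake is the meaning of a significant gene result. Section 2.4.1 presents the pilot as preliminary data for a clinical trial, and a composition effect carried forward as gene regulation would misinform that trial. GSEA is exposed too, since immune gene sets can move together when the mix moves.

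**Working it through.** The plan has no figure of its own to reproduce here. Its goal of 40 comes from pilot-study guidelines, without an effect size, SD or power.

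**Inputs from the documents.** 14 completers (section 2.4.1), taken here as 14 complete blood pairs; paired t-test without covariates (2.4.2); single group (section 2).

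**Assumed inputs.** Lymphocyte fraction f = 0.30 at baseline; lymphocyte-to-other expression ratio r from 1 to 10; mean rise s of 5 or 10 points; SD of the paired log2 difference 0.30, with 0.2 and 0.5 as the range; two-sided alpha 0.05.

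**Step 1: apparent change with no within-cell change.** Bulk B(f) = f·r + (1 − f); apparent change = log2[B(f + s)/B(f)].

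| r | B(0.30) | B(0.35) | B(0.40) | 5-point rise | 10-point rise |
|---|---|---|---|---|---|
| 1 | 1.00 | 1.00 | 1.00 | 0 | 0 |
| 2 | 1.30 | 1.35 | 1.40 | 0.054 log2 (+3.8%) | 0.107 (+7.7%) |
| 5 | 2.20 | 2.40 | 2.60 | 0.126 (+9.1%) | 0.241 (+18.2%) |
| 10 | 3.70 | 4.15 | 4.60 | 0.166 (+12.2%) | 0.314 (+24.3%) |

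**Step 2: comparison with the detectable change.** For n = 14, the noncentral t gives 80% power at a standardised paired change of 0.81. That is 0.81 × 0.30 = 0.243 log2. Only r = 10 with a 10-point rise exceeds it; r = 5 with 10 points (0.241) about equals it; no 5-point case reaches it. At SD 0.2 the threshold is 0.16, and at SD 0.5 it is 0.41, which no scenario reaches.

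**Step 3: rejection rate when no within-cell change exists** (noncentral t, n = 14; nominal 5%).

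| r, rise | SD 0.2 | SD 0.3 | SD 0.5 |
|---|---|---|---|
| 2, 5 points | 16% | 10% | 7% |
| 5, 5 points | 58% | 31% | 14% |
| 10, 5 points | 82% | 48% | 21% |
| 2, 10 points | 46% | 24% | 12% |
| 5, 10 points | 99% | 79% | 39% |
| 10, 10 points | 100% | 95% | 59% |

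**Step 4: what adjustment does.** In simulation (noise SD 0.2 log2, SD of individual shifts 0.06), a 5-point mean shift gives unadjusted false-positive rates of 14%, 38% and 49% for r = 2, 5 and 10. Regressing the log2 change on the change in fraction and testing the intercept returns about 5% if the fraction is known exactly, and about 5% to 10% across the scenarios if it is estimated with error SD 0.03.

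**Step 5: what adjustment costs.** The standard error of the intercept grows by roughly √(1 + n·x̄²/Sxx), with x̄ the mean shift and Sxx = 13 × 0.06² = 0.0468. At 5 points this is √(1 + 14 × 0.0025/0.0468) = 1.32, and at 10 points √(1 + 14 × 0.01/0.0468) = 2.00. Averaged over simulated samples, the factors are 1.4 and 2.1. For a gene with a real within-cell change, r = 1 and 80% unadjusted power, adjusted power is about 76%, 67%, 54% and 29% for mean shifts of 0, 3, 5 and 10 points.

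**The case against.** The strongest objection is that the plan claims nothing about regulation within cells. Section 2.4.2 asks whether two means differ. For whole-blood expression, the paired difference is a legitimate contrast. If the programme itself changes the cell mix, that is a real whole-blood effect, and adjusting for it conditions on a post-intervention variable. This stands, and it is why the unadjusted result should be kept and named for what it is.

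Second, this is a secondary outcome in a small uncontrolled pilot, where cell mix is one of many time-varying causes. That also stands, and it limits the remedy to a sensitivity analysis. It does not remove the point, because this cause can be examined with data already in hand.

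Third, a reader might infer that a shift did occur, or that any shift would be reported as a change in all three genes. The documents do not support this. They give neither a shift nor the cell-type expression of any of the three genes. Entry "between six months and five years past primary treatment" leaves room for counts that are still changing, but it is no evidence that they were.

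A reader might also infer that a change which loses significance after adjustment must be cell mix. Step 5 shows otherwise: real changes often lose significance simply because the interval widens.

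**Conclusion.** The concern holds in conditional form. With whole blood, no differential, covariate-free paired t-tests and no control arm, the plan cannot distinguish a mean shift in leukocyte mix from a change in expression within cells. Bias requires both unequal expression across cell types and a shift in the mean mix, and the documents inform neither.

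Under the assumptions above, the apparent change runs from zero (r = 1) to 0.31 log2. It would be too strong to say that composition alone generally matches what 14 pairs can detect: at SD 0.30 only the 10-point cases with r of 5 or more do so, or nearly. Smaller shifts still matter, since a 5-point rise gives 10% to 48% rejections at that SD for r = 2 to 10.

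For DESeq2/GSEA, the accurate statement is that no adjustment is described, not that none was made. The name of the core laboratory mentions single-cell and CyTOF methods, but the pipeline described is bulk sequencing. The primary outcomes are unaffected.

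**What to change.** Add to section 2.4.4:

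- Neutrophil and lymphocyte scores are estimated for every sample from the existing RNA-seq data, with one published blood signature named before the scores are computed. The mean pre-post change in each score is reported with a 95% CI.
- As a labelled sensitivity analysis, each gene's within-woman log2 change is regressed on the uncentred within-woman change in one score. The intercept and its 95% CI are shown beside the unadjusted mean change. The covariate must not be mean-centred, because the intercept would then just return the unadjusted mean.
- DESeq2 is repeated with that score as a covariate, and the design formula is stated.
- The unadjusted result is kept as the whole-blood effect and described as whole-blood expression, not within-cell regulation.
- Loss of significance after adjustment is not read as evidence of cell mix. Interpretation rests on how far the estimate moves and whether the scores shifted.

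The cost is a few hours of bioinformatics, with no new samples or staff. The downsides are a wider interval (standard error about 1.4 times larger at a 5-point and 2.1 times at a 10-point mean shift, if individual shifts have SD 0.06), imperfectly estimated proportions, and conditioning on a post-intervention variable. It should therefore remain a secondary sensitivity analysis. Even the first item alone would tell readers whether the concern applies.

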2.4.3 Missing Data

Participant responses were reviewed for missing data and participants were given an opportunity to complete overlooked questions or indicate a preference not to answer during the data collection session. All analyses were conducted on participants who completed the intervention. If post-intervention data was unavailable, missing data were not imputed. As a small pilot study to detect trends in change from pre- to post-intervention, we do not expect there to be a systematic bias introduced by the data loss of a small number of participants. One study participant did not complete her post-MM program WAIS-III measure and did not submit her MM logbook due to schedule conflicts.

2.4.4 Secondary Outcomes

Peripheral blood samples were collected before and after the 8-week MM program. The gene expression data was processed and analyzed by the bioinformatics team at the Single-Cell, Sequencing, and CyTOF Core (SC2), Children's Hospital Los Angeles (CHLA), Los Angeles. These data were analyzed using the paired sample t-test in the IBM SPSS Statistics program.

RNA sequencing: Sequencing libraries were prepared from previously purified RNA using the Illumina TruSeq Stranded mRNA Library Prep kit following the manufacturer's instructions. Sequencing was performed on a NextSeq 500 platform using 2 \times 75bp chemistry [39].

Gene Expression data analysis: Quality control and adapter trimming was performed using trim galore (v0.4.2) with default parameters [40]. Reads were aligned to the GRCh38 reference genome and transcriptome using HISAT2, v2.1.0 [41], and transcript quantification was performed using featureCounts, v1.5.1 [42]. Differential expression analysis was performed using the 'DESeq2' R package, v1.16.1, [43] and a rank score calculated

as $-\log_{10}(\text{q-val}) * \text{sign}(\log_2 \text{FoldChange})$ was used as input to the GSEA Preranked tool for pathway analysis [44].

The DESeq2 data were used to identify the gene expression changes over the 8-week MM program. DESeq2 (differential expression sequence) files are TMM (weighted trimmed mean of the log expression ratios - trimmed mean of M values) normalized count per million reads.

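### Pathway significance comes from GSEA Preranked, whose gene-shuffling null ignores co-expression, so the nominal p-values and FDRs for these exploratory results are too small

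*Combined protocol and SAP*

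**What the plan says.** Section 2.4.4 (Secondary Outcomes) describes the RNA-sequencing pipeline. On the gene-level step it says: "Differential expression analysis was performed using the 'DESeq2' R package, v1.16.1, [43] and a rank score calculated". The score is -log10(q) times the sign of the log2 fold change, and it "was used as input to the GSEA Preranked tool for pathway analysis". That clause is all the plan says about pathways. It names no gene-set collection, set size, permutation count, significance level or FDR cut-off, and it makes no allowance for correlation between genes.

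The setting is given elsewhere. Section 2 says: "This was a single-group pilot study testing the effects of 8 weeks of MM practice". Section 2.4.1 says: "Although 27 participants were consented, only 14 completed the study". Section 2.4.3 adds: "All analyses were conducted on participants who completed the intervention". The tissue is whole blood (section 2.4.4: "Peripheral blood samples were collected before and after the 8-week MM program"). The hypothesis-testing plan in section 2.4.2 is separate: for BDNF, NF-κB1 and TP53, "gene expression results were analyzed using the paired sample t-test in SPSS". It states no pathway hypothesis.

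**The concern.** A list with one number per gene carries no expression matrix, participant identifiers or time-point labels. Any reference distribution built from it must come from re-drawing genes, which treats the genes in a set as if they varied independently from woman to woman. In blood they do not: a change in cell mix between two draws, for example, moves many genes together. With at most 14 pairs such chance shifts do not average out. The score of an unchanged but co-expressed set therefore varies more than the scores of shuffled sets, and its p-value is too small.

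The problem lies in the reference distribution. Choosing another ranking score would not remove it.

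At stake is which pathways are described as changed over the programme. Section 2.4.1 places the pilot among studies that collect preliminary data for a clinical trial, so a chance pathway could be carried forward as a target. With a single group, no comparison arm would expose it.

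**Working it through.** **Plan's own figure.** There is none to reproduce, because no pathway error rate is stated. Nominal below means the p-value or FDR that the tool would report.

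**Inputs from the documents.** At most 14 pre/post pairs (sections 2.4.1 and 2.4.3); signed -log10(q) ranking and GSEA Preranked (section 2.4.4).

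**Assumptions, not in the documents.** Set size m = 50 (200 as a sensitivity case); average within-set correlation ρ from 0 to 0.10; nominal p < 0.05; weighted enrichment score; paired t-tests with Benjamini-Hochberg q-values standing in for DESeq2, whose design formula is not given.

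**Step 1: direction.** For a set's mean score, correlation inflates the variance by 1 + (m - 1)ρ, which gene shuffling omits. The real two-sided size is then 2(1 - Φ(1.96/√VIF)). For m = 50:

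| ρ | VIF = 1 + 49ρ | Real size |
|---|---|---|
| 0.01 | 1.49 | 11% |
| 0.02 | 1.98 | 16% |
| 0.05 | 3.45 | 29% |
| 0.10 | 5.90 | 42% |

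This shows direction only. The plan uses neither a mean-type statistic nor a normal score, so its own procedure has to be simulated.

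**Step 2: size with the plan's score.** Simulation with no change in any gene: 14 pairs, several thousand genes (4,000 or 6,000), sets of 50, significance from random gene sets.

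| ρ | Rejections at nominal 5% |
|---|---|
| 0 | 4-5% |
| 0.01 | 6-7% |
| 0.02 | 8-9% |
| 0.05 | 14% |
| 0.10 | 21-22% |

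Other runs with the same score, including one with 3,000 genes, gave 13-16% at 0.05 and 21-25% at 0.10. The test is calibrated at ρ = 0, so correlation causes the excess.

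The FDR moves the same way. The share of unchanged sets of 50 with FDR below 0.05 rose from 0.3% at ρ = 0 to about 4% at 0.05 and 10% at 0.10.

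**Step 3: sensitivity.**
- Larger sets (m = 200): 13% at ρ = 0.01, 19% at 0.02, 33% at 0.05, 36% at 0.10.
- Correlated background (m = 50): with ρ = 0.05, 8-10% at background correlation 0.03 and 7% at 0.04; with ρ = 0.10, 13-14% at background 0.05.
- Unweighted score (the documents do not state the weighting): 22% at 0.05 and 35% at 0.10 in one set of runs. The conclusion does not rest on these.

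**Step 4: does the remedy work?** Pre/post labels were swapped within women and genes re-ranked each time (plan's score, m = 50, two runs per correlation):

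| ρ | Gene shuffling | Label swapping |
|---|---|---|
| 0.05 | 14.1%, 13.4% | 2.2%, 6.3% |
| 0.10 | 24.8%, 23.4% | 2.8%, 2.7% |
| 0.20 | 30.8%, 34.7% | 7.5%, 4.0% |

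The six label-swap results average 25.5/6 = 4.3%. Their scatter is simulation error from few replicates.

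**The case against.** The strongest reply is that the direction is right but the size is uncertain and the consequence limited. Most of that stands.

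- **No stated rate is breached.** A reader might infer that pathways are called enriched far more often than the plan states. The plan states no rate; the comparison can only be with the tool's nominal output.
- **Larger figures belong to other analyses.** The 29% and 42% in Step 1, and the roughly 25% and 36-41% obtained by ranking on t at correlations of 0.05 and 0.10, invite a stronger claim. The plan does not rank on t. Its q-based score has many ties, which dampen the inflation without removing it.
- **The correlation is assumed.** A shift shared by all genes largely cancels when a set is compared with its background, so what counts is correlation in excess of background. With correlated background genes the excess over 5% can be small. Larger sets push the other way.
- **The results are exploratory.** Section 2.4.3 describes a small pilot looking for trends, and pathways occupy one clause. A reader might infer that the clinical outcomes or the three named genes are compromised. They are not, because section 2.4.2 tests them by paired t-test without using this ranking.
- **DESeq2 was not simulated.** This could shift the figures but not the mechanism, since only one score per gene reaches the pathway tool.

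None of this supplies a missing allowance for co-expression, and no other section does.

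**Conclusion.** The concern holds in direction, and its size is conditional. Whenever genes in a set are more correlated with each other than with the background, the nominal pathway p-values and FDRs from section 2.4.4 are too small. For sets of 50 the real rate at nominal 5% ranges from barely raised (6-7% at correlation 0.01) to about four times nominal (21-22% at 0.10). A correlated background brings the upper end down to 13-14%, and sets of 200 raise the rate to about 33% already at correlation 0.05. These figures rest on assumed correlations and set sizes, the weighted enrichment score and a stand-in for DESeq2.

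The documents do not show that any particular pathway was falsely reported, since they contain no pathway results and no decision rule. The point is worth correcting, but it is confined to the exploratory secondary pathway analysis.

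**What to change.** Keep the Preranked enrichment score as a descriptive summary. Take pathway p-values and FDR from one of:

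1. a null that swaps pre/post labels within each woman and re-ranks all genes at every swap. Fourteen pairs allow 2^14 = 16,384 swaps, and 1,000 or more random ones suffice. A fast paired gene-level statistic may replace repeated DESeq2 fits; or
2. a correlation-adjusted gene-set test, such as CAMERA, with participant in the design.

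State the gene-set collection, set-size limits and FDR cut-off. Label any Preranked p-values still shown as unadjusted for co-expression. If no re-analysis is done, that label, with the pathway results called descriptive, is the minimum.

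The cost is some re-analysis of existing counts and a few sentences in section 2.4.4, with no new samples or visits. Fewer pathways will be significant. Neither option makes up for the missing control group: a pathway that passes shows change over the 8 weeks, not an effect of the programme.
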